# 8.5 Follow-up

# 8.5.1 Survival Follow-up

Survival follow-up will be performed after the end-of-treatment visit (including patients who discontinue treatment early due to intolerance). Patients will be re-examined every

6 months and followed up for 2 years from the end of treatment.

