## 4.4 Follow-up

Patients who withdraw from the study due to intolerable AEs will be followed up in this study until the events resolve to Grade 1 or lower, or the AE is stable. Patients will be followed up for up to 24 months after completion of the treatment, or until study termination, PD, initiation of new anti-tumor therapy, or death.

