# 5.4 Removal of Patients from Therapy or Assessment

Efforts must be made to complete the efficacy and safety tests at the time of treatment discontinuation as specified in the protocol, and to complete safety follow-up, with complete documentation of AEs and outcomes. The investigator may recommend or provide new or alternative treatments to the patient according to the actual conditions. Patients with non-PD should continue to be followed up for efficacy evaluation until they start a new antineoplastic therapy or have PD.

If a patient refuses to visit the study site for further visits, he/she should continue to be followed up for the collection of information about the study unless he/she withdraws consent to disclose further information or be contacted. In this case, no further evaluation should be conducted and no further information should be collected.

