# **8.4** Early Withdrawal (Discontinuation of Study Treatment)

### Three months after the Last Treatment:

- Physical examinations
- Vital signs measurements (body temperature, pulse, systolic and diastolic blood pressure, and respiratory rate)
- ECOG performance status
- Disease-related signs and symptoms
- Assessment and recording of AEs
- Hematology: Hemoglobin, ANC, WBC count, platelets
- Blood chemistry: Serum glucose, AST, ALT, total bilirubin, creatinine, Na, K, uric acid, total protein, and albumin
- Serum LDH
- Serum immunoglobulin quantification
- Urinalysis and stool
- Detection of LGLs in peripheral blood
- Detection of peripheral blood lymphocyte subsets (B/T/NK; Treg; T-cell immune function; TH1/TH2)
- Peripheral blood flow cytometry
- Peripheral blood TCRvβ flow cytometry
- Bone marrow smear, bone marrow biopsy, and immunohistochemistry
- Chromosome karyotype examination in bone marrow or peripheral blood
- ECG
- Evaluation of measurable lesions (including neck, chest, abdomen, and pelvis) by CT in patients with lymph node enlargement before admission
- Assessment of cardiac function and ejection fraction by two-dimensional echocardiography; abdominal color Doppler ultrasound, etc.
- Coagulation function

Following this assessment, patients will be followed up twice a year until the EOS, including survival, disease status, and long-term toxicity.

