# 2. Secondary Efficacy Endpoints

• Response rates: ORR and PR rate (time frame: 24 months after the last treatment)

Point estimates of rates will be calculated for each protocol analysis set. An estimate of the 95% CI for the response rate will also be derived. Graphical and descriptive analyses will be used to explore associations between relevant markers and responses.

• PFS and OS (time frame: 24 months after the last treatment)

Time from the first day to PD or death from any reason. The median duration of the overall response will be assessed with a 95% CI.

• DoR (time frame: 24 months after the last treatment)

The time when CR or PR is met until the first date of recurrent or progressive disease. The median duration of the overall response will be assessed with a 95% CI.

• Effect of biomarkers on efficacy and adverse reactions

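### The protocol ends follow-up of early stoppers in four different ways; under 8.5.1 its length depends on how treatment went, so Kaplan-Meier PFS and OS after about month 27 may be biased.

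*Supplement*

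**What the plan says.** All references are to protocol version 2.0.

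- **8.4 (Early Withdrawal):** after the assessment three months after last treatment, "patients will be followed up twice a year until the EOS, including survival, disease status, and long-term toxicity".
- **8.5.1 (Survival Follow-up):** "Survival follow-up will be performed after the end-of-treatment visit (including patients who discontinue treatment early due to intolerance"; these patients are re-examined every "6 months and followed up for 2 years from the end of treatment".
- **9.3 (Secondary Efficacy Endpoints):** "PFS and OS (time frame: 24 months after the last treatment". PFS itself is counted from the first day of study (9.2).
- **4.4 (Follow-up):** "Patients will be followed up for up to 24 months after completion of the treatment, or until study termination, PD, initiation of new anti-tumor therapy". Follow-up ends at death as well.
- **5.4 (Removal of Patients):** "Patients with non-PD should continue to be followed up for efficacy evaluation until they start a new antineoplastic therapy or have PD". No time limit is given.
- **4.8 (Study Termination):** EOS is the last patient's last visit at the end of the follow-up period, yet it is expected about 2 years after the last patient enrolls.

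Enrollment is expected to take 2 years (4.3) and thalidomide runs for up to 2 years (4.2). PFS and OS are summarised descriptively by Kaplan-Meier, with the detailed rules left to an SAP (11.3).

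**The concern.** The same early stopper has several possible end dates. Sections 8.4 and 8.5.1 cannot be read as one rule for early withdrawals and another for completers, because 8.5.1 expressly covers patients who stop early for intolerance. Sites could follow different rules in good faith.

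The 8.5.1 rule also has a statistical consequence. PFS and OS start at the first day, but observation ends 24 months after each patient's own last dose. Length of observation is therefore set by treatment duration, and duration depends partly on outcome: intolerable toxicity and lack of benefit are both reasons to stop (5.3, 6.1). Kaplan-Meier assumes that censoring carries no information about later risk. If early stoppers differ in prognosis from completers, the later part of the curve describes mainly the patients who stayed on treatment.

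For OS, 4.4 may act sooner still. If it governs survival follow-up, patients who progress, or who move to second-line treatment after 6 months without benefit (6.1), could leave observation at that point.

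**Working it through.** The plan gives no figure of its own on this point, so there is none to reproduce. The inputs from the documents are 24 months of enrollment, up to 24 months of treatment, 24 months of follow-up after treatment, and 42 enrolled patients. The share of early stoppers and their prognosis are not given and are assumed below.

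**Step 1. End of observation under 8.5.1.** Month of leaving = stop month + 24.

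- stop at month 3: 3 + 24 = 27
- stop at month 6: 6 + 24 = 30
- stop at month 12: 12 + 24 = 36
- completer at month 24: 24 + 24 = 48

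**Step 2. End of observation under 8.4.** This depends on when EOS falls. Let e be the month of enrollment, 0 to 24.

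- *EOS 24 months after last enrollment (the timing 4.8 expects):* observation = 48 - e, so 48 months for the first patient and 24 for the last. Section 8.4 is longer than 8.5.1 only if 48 - e > stop + 24, that is e < 24 - stop: before month 21 for a month-3 stop, before month 18 for a month-6 stop. For later enrollees 8.4 is shorter.
- *EOS after the last patient's full 24 + 24 months (one reading of the 4.8 definition):* observation = 72 - e, so 72 down to 48 months. Section 8.4 is then longer for every early stopper.

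**Step 3. Effect on Kaplan-Meier at month 48, closed form.** Let f be the share of early stoppers, S1 and S2 the 48-month event-free rates of long-treated patients and early stoppers, h1 and h2 the matching exponential hazards, and c = stop + 24.

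- True value: (1-f)·S1 + f·S2
- Kaplan-Meier limit: [(1-f)·exp(-h1·c) + f·exp(-h2·c)] · exp(-h1·(48-c)), because after month c only long-treated patients remain at risk

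| f | S1/S2 | stop | true | Kaplan-Meier | shift (points) |
|---|---|---|---|---|---|
| 0.2 | 70/30% | 3 | 62.0% | 64.7% | +2.7 |
| 0.3 | 70/30% | 3 | 58.0% | 62.0% | +4.0 |
| 0.1 | 60/20% | 6 | 56.0% | 57.0% | +1.0 |

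These cases assume a large difference in prognosis: ln 0.3 / ln 0.7 = 3.4 and ln 0.2 / ln 0.6 = 3.2 times the hazard.

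**Step 4. Varying the hazard ratio.** A large-sample simulation (400,000 patients) used exponential times with medians of 36, 60 and 120 months for long-treated patients, 10-30% early stoppers and stops spread over months 3 to 6. It compared 8.5.1 censoring with follow-up of everyone to month 48.

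| hazard of early stoppers relative to others | shift at month 48 (points) |
|---|---|
| 0.5 | -0.5 to -3.2 |
| 1 | 0 |
| 1.5 | +0.4 to +1.6 |
| 2 | +0.7 to +2.4 |
| 3 | +0.7 to +3.3 |

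There is no shift at month 24 in any scenario.

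**Step 5. Scale.** With 42 patients and an estimate of 62%, the standard error ignoring censoring is √(0.62 × 0.38 / 42) = 0.075, or about 7.5 points.

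**The case against.** The strongest reply is that this is a wording matter on descriptive secondary endpoints of a single-arm trial. No 3- or 4-year rate is planned, only Kaplan-Meier summaries and a median with confidence interval. The possible shift is well below the standard error. Patients who stop for progression already have their PFS event, and 5.4 would keep event-free stoppers under efficacy follow-up without a time limit, so the PFS risk set need not shrink at months 27 to 30. Censoring rules are left to an SAP that is not shown.

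Most of this stands and limits the size of the point. It does not remove it. Section 5.4 is one of four conflicting rules, and nothing says it prevails over 8.5.1. An SAP can decide how to censor, but it cannot recover follow-up that was never collected.

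Three stronger readings are tempting but unsupported:

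- A reader might infer that later estimates are biased upward as a matter of fact. The documents give neither the number nor the prognosis of early stoppers, and the direction turns on that.
- A reader might take months 27 to 30 as a general limit. They apply to stops at months 3 to 6 only; a stop at month 12 leads to month 36.
- A reader might infer that 8.4 always gives longer follow-up, up to month 72. That needs EOS to wait for the last patient's full treatment and follow-up, and it conflicts with the timing that 4.8 expects.

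**Conclusion.** The inconsistency is real in the current version and should be reconciled. Under 8.5.1, censoring time depends on the course of treatment, so Kaplan-Meier PFS and OS after about month 27 may be biased. The shift at month 48 is upward by roughly 0.4 to 4 points if early stoppers fare worse, under assumed exponential times, 10-30% early stoppers and 1.5 to 3.4 times the hazard. It is zero with equal hazards, and downward by 0.5 to 3.2 points at half the hazard. PFS is affected only through patients who stop without an event. The earlier loss from the OS risk set that 4.4 could cause is not quantified here. The primary complete remission rate is unaffected. The point merits correction because the remedy is cheap and the lost follow-up cannot be regained once patients have been released.

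**What to change.** Reconcile 4.4, 4.8, 5.4, 8.4, 8.5.1 and 9.3 into one rule: every treated patient, whenever and for whatever reason treatment stops, is followed every 6 months to the same time from first dose. For survival, this continues after progression or new therapy. State the PFS/OS time frame in 9.3, and its copy in the synopsis, from first dose.

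Follow-up until EOS is an acceptable alternative only if the definition and expected timing of EOS in 4.8 are first made consistent. On the timing now expected, it would shorten follow-up for late enrollees.

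The cost is wording, plus some additional six-monthly contacts for early stoppers.

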## 8.5.2 Safety Follow-up

Safety follow-up will be performed for all patients who complete or discontinue treatment until 1 year after the last dose of the study drug, or until initiation of a new antineoplastic therapy (whichever occurs first).

Patients will be contacted by phone 1 year after the last dose, or asked to the study site for a safety visit to collect the ongoing AEs or changes in laboratory abnormalities, and to assess new AEs, SAEs, new concomitant medications, or changes in current medications since the last assessment. Any new conditions that occur during the safety follow-up need to be documented in the CRF as appropriate. After the safety follow-up (ie, 28 days after the last dose), there is no need to actively collect AEs. However, if an SAE occurs and the investigator assesses a reasonable causality to the study drug, the SAE should be reported.

AEs (regardless of causality) that do not completely resolve at the end of safety followup must be followed up until recovery (chronic, baseline value, or completely recovery), or clinical stability is achieved.

# 9. Efficacy Evaluation

## 9.1 Definition

### 9.1.1 General Definition

Evaluable toxicity: All patients who have received at least 1 month of TPM treatment are evaluable for toxicity evaluation from the first treatment.

Evaluable objective response: Only patients who have a measurable disease at baseline, have received at least 1 treatment cycle, and have been re-evaluated for the disease will be considered as evaluable responses. These patients will be categorized for their responses according to the following definitions (Note: Patients who demonstrate objective PD or death by the end of Cycle 1 will also be considered evaluable).

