## 4.5 Sample Size

A retrospective study of 45 patients is used as the historical control, in which cyclophosphamide monotherapy was applied with an effective rate of 72% and CRR of 47%. From the perspective of clinical expertise, taking the CRR of 70% as the minimum threshold for clinical significance, the sample size of 35 patients in this group is deemed sufficient to test the overall true CRR that is superior to that of the historical control at a false positive rate  $\alpha = 0.05$  (two sides) and false negative rate  $\beta = 0.2$  (ie, power = 80%). With a 20% dropout rate, at least 42 patients would be required to enroll in this study.

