# 6 Treatments

# **6.1 Treatment Regimen**

Treatment will be provided in 3-month cycles. Patients will receive thalidomide of 50 to 100 mg orally QD before bedtime, methotrexate of 10 mg/m² orally once weekly, and prednisone of 0.5 to 1 mg/kg orally QOD. Prednisone will be tapered after 3 months of dosing and dosed for up to 6 months. Methotrexate will be dosed for up to 1 year. Thalidomide will be dosed for up to 2 years or discontinued at the investigator's discretion based on clinical symptoms. Efficacy was evaluated after 3 months of treatment, if PR or above response to treatment, the initial treatment regimen will be continued. If there is no clinical benefit after 6 months of initial treatment, patients will switch to the second-line treatment was and will be withdrawn from the study.

Dosage and administration for study drugs are shown in the following table:

TPM Regimen	Dosage and Administration
Methotrexate	10 mg/m  orally, once weekly
Prednisone	0.5–1 mg/kg orally, every other day
Thalidomide	50–100 mg orally, once daily before bedtime

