# 8.1 Screening Period

All patients will undergo study eligibility screening, which will be completed within 4 weeks before the start of the study, including:

- Review of inclusion/exclusion criteria
- Physical examinations
- Vital signs measurements (body temperature, pulse, systolic and diastolic blood pressure, and respiratory rate)
- Height, weight, and body surface area
- ECOG performance status
- Disease-related signs and symptoms
- Assessment and recording of serious pre-treatment events
- Complete medical history (previous treatment and efficacy, enlargement of liver, spleen and lymph nodes; presence of other comorbidities)
- Hematology: Hemoglobin, ANC, WBC count, platelets
- Blood chemistry: Serum glucose, AST, ALT, total bilirubin, creatinine, Na, K, uric acid, total protein, and albumin
- Serum lactate dehydrogenase (LDH)
- Serum β2 microglobulin
- Serum immunoglobulin quantification
- Serological tests for HIV, hepatitis C virus (HCV), and HBV (including hepatitis B surface antigen [HBsAg], anti- hepatitis B surface antibody [HBsAb], and anti-hepatitis B core antibody [HBcAb])
- HBV-DNA and HCV RNA: HBV-DNA and HCV RNA will be used in patients with serologically positive HBV or HCV, respectively
- Coagulation function (8 items)
- Detection of peripheral blood lymphocyte subsets (B/T/NK; Treg; T-cell immune function; TH1/TH2)

- Peripheral blood flow cytometry
- Pregnancy test (if applicable)
- Urinalysis and stool
- Bone marrow aspiration and biopsy
- Bone marrow smear, immunohistochemistry, and flow immunophenotyping
- Flow cytometry detection of LGLs in patient's bone marrow fluid or peripheral blood; flow cytometry detection of killer immunoglobulin-like receptor; TCR rearrangement; TCRvβ flow cytometry, karyotyping; next generation sequencing
- Electrocardiograph (ECG)
- Computed tomography (CT) for assessment of measurable lesions (including neck, chest, abdomen, and pelvis)
- Assessment of cardiac function and ejection fraction by two-dimensional echocardiography; abdominal color Doppler ultrasound, etc.

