# 9.2 Efficacy Evaluation

The evaluation will be started from Month 3. Hematologic ORR is defined as the sum of CR and PR.

Hematologic CR: Clinical symptoms and signs turn normal (splenomegaly disappears), and blood cell count completed turn normal, ie, hemoglobin >110 g/L, platelets >100 ×  $10^9$ /L, ANC >1.5 ×  $10^9$ /L, lymphocyte count <4 ×  $10^9$ /L, and LGLs in peripheral blood are within the normal range (<0.5 ×  $10^9$ /L).

Complete molecular response: No LGLs can be detected when reaching CR (negative TCR rearrangement by flow cytometry or polymerase chain reaction [PCR]).

Hematologic PR: Hematologic PR is defined as blood cell count that do not meet criteria for CR but improvement is observed, such as neutrophil counts  $>0.5 \times 10^9/L$  without repeated infection, an increase of hemoglobin level from baseline by more than 20 g/L without blood transfusion, platelets  $>50 \times 10^9/L$ .

SD: CR/PR criteria are not met after standardized treatment for 4 months, but no significant progression is observed.

PD: Cytopenia (hemoglobin decreased by 2 g/dL, <10 g/dL; ANC decreased by  $0.5 \times 10^9$ /L, <1.0 ×  $10^9$ /L; platelets decreased by  $20 \times 10^9$ /L, <100 ×  $10^9$ /L, requiring blood transfusion) or progressive worsening of organomegaly.

PFS: PFS is defined as the time from the first day of study to PD or death, including PD and death from any cause (eg, PD, toxicity, unrecorded progression in a new treatment, or death).

DoR: DoR is defined as the time when CR or PR is met until the first date of recurrent or progressive disease.

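### The only response population in the protocol leaves out patients who stop before Month 3 for toxicity, refusal or loss, and if the CRR is computed in it the rate is biased upward

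*Supplement*

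**What the plan says.** All references are to protocol version 2.0.

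- **Response population (9.1.1).** Response is evaluable in "Only patients who have a measurable disease at baseline, have received at least 1 treatment cycle, and have been re-evaluated for the disease". The section continues: "These patients will be categorized for their responses according to the following definitions". The one exception is: "Patients who demonstrate objective PD or death by the end of Cycle 1 will also be considered evaluable".
- **Timing.** Section 6.1: "Treatment will be provided in 3-month cycles". Section 9.2: "The evaluation will be started from Month 3".
- **Primary endpoint (9.3) and its analysis (11.3).** The endpoint is the CRR of symptomatic patients treated with the regimen, reported as a point estimate with an exact 95% binomial interval. Neither section names an analysis set for it.
- **Analysis sets.** The only mention is in the secondary endpoints of 9.3 (and the matching synopsis text), under ORR and PR rate: "Point estimates of rates will be calculated for each protocol analysis set". The sets are not defined. Section 11.3 refers the rules for DoR, PFS and OS to the SAP, but not the CRR denominator.
- **Sample size (4.5).** 35 patients are planned to test a CRR of 70% against a historical 47%, at two-sided alpha 0.05 and 80% power. Then: "With a 20% dropout rate, at least 42 patients would be required to enroll in this study".
- **Ways out before Month 3 (5.3).** These include intolerable toxicity, unwillingness to continue and loss to follow-up.

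**The concern.** A patient who stops at, say, week 6 because of toxicity has not received one cycle and has reached no scheduled response assessment. Under 9.1.1 that patient gets no response category. Progression and death are kept by the exception, but toxicity, refusal and loss are not. For a regimen whose tolerability is itself under study, an early toxicity stop is a failure of treatment, and removing it shrinks the denominator without touching the numerator.

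What is at stake is the trial's one benchmark comparison, the CRR against 47%. A rate among patients who stayed three months is not the rate for patients who were started on the regimen, and a test against 47% no longer has its stated error rate for the all-treated question.

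A smaller problem in the same sentence is the condition of measurable disease at baseline. Elsewhere the protocol uses the word measurable for lesions on CT (8.1: "Computed tomography (CT) for assessment of measurable lesions"). Three of the seven treatment indications in 5.2.1 are cytopenias, and CR in 9.2 rests on symptoms and signs, blood counts, LGL count and spleen. It is unclear whether a patient with cytopenia only meets the condition.

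**Working it through.** **1. The plan's own figures.** With p0 = 0.47, p1 = 0.70, two-sided alpha 0.05 and power 80%, the one-sample normal approximation is

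n = [1.960·√(0.47·0.53) + 0.842·√(0.70·0.30)]² / (0.70 − 0.47)² = 35.16,

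which agrees with the stated 35. The 42 is 35 × 1.2. Dividing by 0.8 instead gives 43.75, that is 44. Either way, the allowance is meant to leave about 35 patients for analysis, which fits an analysis that omits dropouts. Losing 20% of 42 leaves 33.6, taken as 34.

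**2. Direction of the bias.** Let d be the share of treated patients who leave before Month 3 by a route other than progression or death. Assume that none of them has a CR, since scoring starts at Month 3. Then

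evaluable CRR = all-treated CRR / (1 − d),

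which exceeds the all-treated CRR whenever d > 0.

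**3. False-success rate.** Success means that the lower exact 95% limit exceeds 47%, that is, an exact one-sided test at 2.5%. For m evaluable out of 42, c is the smallest count with P(X ≥ c) ≤ 0.025 for X ~ Bin(m, 0.47). The true all-treated CRR is set at 47%, so the evaluable rate is 0.47 × 42/m.

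| Lost early | m | c | Evaluable CRR | P(false success) |
|---|---|---|---|---|
| 0 | 42 | 27 | 47.0% | 1.8% |
| 2 | 40 | 26 | 49.3% | 3.4% |
| 4 | 38 | 25 | 51.9% | 6.0% |
| 8 | 34 | 23 | 58.1% | 16.9% |

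The protocol does not say how the 20% divides before and after Month 3. Eight early losses means all of it comes early, so the last row is the upper end.

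**4. The same data under two denominators (8 lost early).** With 24 CRs:

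- 24/34 = 71%, exact 95% CI 53–85%, excludes 47%;
- 24/42 = 57%, exact 95% CI 41–72%, includes 47%.

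**5. Power with all 42 in the denominator.** At least 27 CRs are needed. If the all-treated CRR is 70%, power is 84%. If 70% holds only among evaluable patients, the all-treated CRR is 0.70 × m/42:

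| Lost early | All-treated CRR | Power |
|---|---|---|
| 2 | 66.7% | 69% |
| 4 | 63.3% | 52% |
| 8 | 56.7% | 20% |

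**The case against.** **The link to the primary analysis is inferred.** No sentence says that the CRR is computed in the 9.1.1 population. The endpoint wording in 9.3 would fit an all-treated denominator, and the mention of analysis sets suggests that more than one is intended. A reader might infer that the plan prescribes the restricted denominator for the CRR; the documents do not go that far. What stands is that 9.1.1 is the only response population defined, that it alone says who receives a category, and that no rule counts unassessed patients as non-CR.

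**A SAP is mentioned but not shown.** It may define the sets, so their absence from the protocol carries no weight here. But 9.1.1 is a stated restriction, and 11.3 sends only the time-to-event rules to the SAP.

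**The 17% is an extreme.** Treatment runs up to 24 months and follow-up another 24, so much of the dropout may fall after Month 3, and early exits by progression or death are kept. Section 2.6.2 reports a single Grade 3 reaction in the preliminary data. This stands: 17% is a ceiling.

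**The benchmark's denominator is unknown.** If the historical 47% was itself a rate among evaluable patients, a like-for-like distortion would be smaller. This also stands.

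**The data could be rebuilt.** Section 11.1 has excluded and dropout patients described one by one, and 5.4 asks for efficacy tests at discontinuation. A reader could recover the all-treated rate, but that does not settle which rate is primary.

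**Measurable disease may be loose wording.** Blood counts are measurable too, and the CT passages speak of lesions rather than disease. That the rule removes every patient with cytopenia only is a reading the text permits but does not establish.

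**Conclusion.** The point holds in this form: the CRR denominator is unnamed, and the only response population on offer would bias the CRR upward by leaving out early stops for toxicity, refusal or loss. It would be too strong to say that only patients completing a full cycle are counted, because progression and death by the end of Cycle 1 stay in.

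The direction rests on early leavers having no CR, which follows from the Month 3 start of scoring. The size rests on the unknown number of early losses and on reading 47% as an all-treated rate. With two losses the effect on the error rate is modest; with four it is more than twice the nominal 2.5%; with eight the choice of denominator can reverse the conclusion. Because this is the primary endpoint, the denominator should be fixed before the data are analysed.

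**What to change.** - **9.1.1 and 11.3:** name as the primary CRR denominator all eligible patients who received at least one dose of any study drug, and count anyone without a documented CR, including anyone not re-evaluated, as non-CR.
- **Sensitivity analysis:** keep the one-cycle evaluable set, with the number and reasons for exclusion.
- **Measurable disease:** delete the condition, or replace it with the entry indications of 5.2.1, so that patients with cytopenia only are clearly included.
- **4.5:** state that 70% is an all-treated rate, or restate the power.

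The cost goes beyond wording. The reported CRR will be lower wherever there are early losses. If 70% is an all-treated rate, 42 patients still suffice (27 CRs needed, 84% power). If 70% was meant for evaluable patients, the 80% is not reached, as step 5 of the working shows, and either the power statement or the sample size has to be revisited.
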